This Statistical Analysis Plan (SAP) provides detailed statistical methodology for the analysis of data from study VAY736Y2102 that will be presented in the Clinical Study Report (CSR). The output shells accompanying this document can be found in the Tables, Figures and Listings (TFL) shells document. The specifications for derived variables and datasets can be found in the Programming Datasets Specifications (PDS) document. This version of the SAP is based on the Protocol Version 06 released on 20-Oct-2021.

All required changes to the planned analysis described in this document will be made through an amendment or addendum, depending on whether the change is made before or after database lock (DBL), respectively. Note that obvious corrections will be made at the time of analysis to address minor formatting or spelling mistakes present in the TFL shells document, without the need to amend.

The SAP, TFL shells and PDS documents may also serve as a reference for the creation of any outputs required outside of the CSR, e.g., maximum-tolerated dose (MTD) or recommended dose for expansion (RDE) declaration, Investigator's Brochure (IB) updates, abstracts, posters, presentations, manuscripts, and management updates. Data used for these analyses will have a status aligned to the database lock guidance.

The CVAY736Y2102 trial has been endorsed for early termination by the ICDB on 22-Sep-2023, due to business purposes and not safety concerns.

1.1 Study design

This Phase Ib, multi-center, open-label study has two parts: a dose-escalation part and a dose-expansion part. The purpose of the dose-escalation part is to characterize the safety and tolerability of VAY736 in combination with ibrutinib in patients with relapsed, refractory chronic lymphocytic leukemia (CLL). The dose-escalation part will be guided by a Bayesian Logistic Regression Model (BLRM) to estimate the MTD and/or RDE of the combination.

[figure not shown]
Upon identification of the MTD or RDE, a dose-expansion part will be opened to patient enrollment to further characterize the safety, pharmacokinetics (PK), and pharmacodynamics (PD), if available, and preliminary anti-tumor efficacy of the combination.

Both the dose escalation and dose expansion parts will enroll patients with CLL who are currently receiving ibrutinib therapy following relapse on another approved therapy AND have either failed to achieve a CR after > 1 year of ibrutinib treatment OR who have developed a resistance mutation to ibrutinib without clinical relapse at any time during treatment. The dose expansion part of the study will also include patients who have received ibrutinib either alone or in combination (or have received ibrutinib continuously with multiple sequential combination partners) as first-line therapy and have either failed to achieve a complete response after 1 year of therapy or have developed a resistance mutation to ibrutinib. Approximately 15-20 patients will be enrolled to the dose escalation part of the study. In the expansion part, approximately 40 patients will be enrolled to two arms (approximately 20 patients in each arm). One arm will enroll patients who have been on ibrutinib treatment for more than one year with evidence of residual disease which places them at risk for clinical relapse; the other arm will enroll patients with acquired resistance mutations to ibrutinib who have not yet demonstrated

clinical relapse, see [Figure 1-1](#). All patients with acquired resistance mutations will be enrolled in Arm B, irrespective of ibrutinib treatment duration.

As of Protocol Version 06, enrollment to Arm B (patients with BTK inhibitor resistance mutation) is closed due to slower than anticipated enrollment.

Figure 1-1 Study design

* Combination administered for either 6 cycles or 8 cycles, ibrutinib continued through C8D28. For patients who achieve a CR at the primary endpoint (C9D1), investigators may consider discontinuing ibrutinib.

**Patients will be evaluated for the final disease assessment on C9D1 (\pm 7 days) in accordance with IWCLL guidelines.

1.2 Study objectives and endpoints

Objectives and related endpoints are described in [Table 1-1](#) below.

Table 1-1 Objectives and related endpoints

Objective	Endpoint	Analysis
Primary		Refer to Section 2.6
To determine the MTD and/or RD of the combination of VAY736 with ibrutinib	Safety Escalation only: 
Incidence of DLTs in cycle 1 (28 days)	
To characterize the safety and tolerability of the combination of VAY736 and ibrutinib	Escalation and expansion: 
Incidence and severity of AEs and SAEs, including changes in laboratory parameters and vital signs Tolerability Dose interruptions, reduction, and dose intensity	
Secondary		Refer to Section 2.8
To assess any preliminary antitumor activity of the combination	Rate of patients with CR/CRI assessed by investigators per IWCLL at cycle 9 day 1 Overall response rate (ORR) assessed by investigators per IWCLL criteria and Time To Progression (TTP)	
	Clearance of ibrutinib resistance mutations (BTKC481 and/or PCLy2 hotspot), defined as less than 1% mutation bearing alleles (Arm B only).	
To characterize the PK of VAY736 and ibrutinib when used in combination therapy	Plasma concentration of VAY736 and ibrutinib, and derived parameters	
To assess immunogenicity (IG) following one or more intravenous infusions of VAY736	Presence of anti-VAY736 antibodies	

Objective	Endpoint	Analysis

2 Statistical methods

2.1 Data analysis general information

Study data will be analyzed by Novartis personnel and/or designated CRO(s) using the most updated SAS® version in the GPS environment. For Bayesian modeling, R (version 3.2.3) and/or JAGS (version 4.6.0) will be used. PK parameters will be calculated using non-compartmental methods available in Phoenix WinNonlin version 8.3 (or latter version if available).

The study data will be analyzed and reported (in a primary CSR if final DBL has not occurred) based on all patients' data from the dose escalation and dose expansion parts up to the time when all patients have completed at least six cycles of combined treatment with VAY736 and ibrutinib and two cycles of ibrutinib alone or have discontinued the study. The primary CSR will include all outputs planned within the TFL shell document. Additional data for patients continuing to receive study treatment past the data cutoff date of the primary CSR, as allowed by the protocol, will be reported once all patients have discontinued the study. However, only a selection of key outputs (indicated in the TFL shell document) for which additional data was collected will be provided for the final report.

Data from participating centers in this study protocol will be combined, so that an adequate number of patients will be available for analysis. No center effect will be assessed. The data will be summarized with respect to demographic and baseline characteristics, efficacy observations and measurements, safety observations and measurements. All relevant pharmacokinetic (PK) measurements will also be summarized. The summaries will use descriptive statistics for quantitative data and contingency tables (frequencies and percentages) for qualitative data.

In case of intra-subject dose escalation, patient's data from before and after the change in dose will be listed and summarized together under the originally intended dose level/treatment group.

A treatment is defined by the dose level (corresponding to a single combination of doses of VAY736 and ibrutinib) and regimen. During the initial dose-escalation phase of the study, in which the dose of VAY736 will be escalated in combination with a fixed dose of ibrutinib, cohorts of patients with the same treatment will be pooled into one single *treatment group*. Thus, a treatment group may consist of more than one cohort. Patients receiving the same dose of VAY736 under different regimens, Q2W or Q4W, belong to different treatment groups. Specific plans regarding a change in dosing regimen are discussed in [Section 2.6.1.1](#) of the SAP.

Patients treated with the same dose level and schedule of VAY736 will be pooled, for all safety analyses including PK and ADA, into a single treatment group (which may include patients from both the dose-escalation and dose-expansion parts).

For efficacy analyses, data will also be summarized by study part, and within each study arm of the dose expansion part. If multiple dose regimens are observed, summaries will also be produced within each treatment regimen as follows:

- Study parts: dose escalation, dose expansion
- Study arms:

- Dose expansion part:
 - Study arm A (~20 pts): patients with advanced CLL who have been on ibrutinib treatment for more than one year with evidence of residual disease and which places them at risk for clinical relapse.
 - Study arm B (~20 pts): patients with acquired resistance mutations to ibrutinib who have not yet demonstrated clinical relapse.

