6.2.2 Provisional dose levels

[Table 6-2](#) describes the starting dose and the dose levels of VAY736 that may be evaluated during this trial. Ibrutinib will be administered at 420 mg daily during dose escalation. During the dose expansion part of the study, ibrutinib will be continued at the same dose schedule as tolerated before study enrollment.

[REDACTED]

Table 6-2 VAY736 provisional dose levels

Dose level	Proposed dose of VAY736*
-1**	0.1 mg/kg
1	0.3 mg/kg
2	1 mg/kg
3***	3 mg/kg

*Proposed dose regardless of whether Q2W or Q4W regimen is used. It is possible for additional and/or intermediate dose levels to be added during the course of the study. Cohorts may be added at any dose level below the MTD in order to better understand safety, PK, or PD.

**Dose level -1 represents treatment doses for patients requiring a dose reduction from the starting dose level. No dose reduction below dose level -1 is permitted for this study.

***If clinically indicated, dose levels higher than 3.0 mg/kg may be investigated.

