6.2.3 Guidelines for dose escalation and determination of MTD/RD

The MTD is defined as the highest combination drug doses not expected to cause DLT in 33% or more of the treated patients in the first cycle of treatment. Adverse events and laboratory abnormalities considered to be DLTs are defined in [Table 6-3](#). This MTDs or a lower dose combination will then be selected as the RD(s).

The BLRM provides an estimate of the combination of VAY736 and ibrutinib not exceeding the MTD. Typically the MTD is the highest tested combination with less than 25% risk of excessive toxicity (see [Section 10.4.2](#)).

The Recommended Dose (RD) will be a dose that is less than or equal to MTD and has, in the view of the investigators and Novartis study personnel, the most appropriate benefit-risk assessment based on the review of safety and tolerability, PK, PD, and activity information. Note, that it is possible that the MTD may not be reached in some situations.

For the purposes of dose escalation decisions, each cohort will consist of 3 to 6 newly enrolled patients who will be treated at the specified dose level. The first cohort will be treated with the starting dose of 0.3 mg/kg i.v. Q2W of VAY736 in combination with 420 mg of ibrutinib daily.

Patients must complete a minimum of 1 cycle of treatment with the minimum safety evaluation and drug exposure or have had a DLT within the first cycle of treatment to be considered evaluable for dose escalation decisions. Dose escalation decisions will occur when the cohort of patients has met these criteria and a minimum of three patients are determined to be evaluable. If only 2 patients in a cohort are evaluable and neither subject has experienced a treatment-related clinically significant non hematological toxicity > CTCAE grade 1, dose escalation decisions may be considered.

Dose escalation decisions will be made by Investigators and Novartis study personnel. Decisions will be based on a synthesis of all relevant data available from all dose levels evaluated in the ongoing study including safety information, DLTs, all CTCAE Grade \geq 2 toxicity data during Cycle 1, PK, and PD data from evaluable patients. The recommended dose for the next cohort of subjects will be guided by the Bayesian logistic regression model (BLRM) with EWOC principle.

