6.2.3.2 Intra-Patient dose escalation

Intra-patient dose escalation is not permitted at any time within the first two cycles of treatment. After the second cycle is completed, individual patients may be considered for treatment at a dose of VAY736 that is higher than the dose to which they were initially assigned. In order for a patient to be treated at a higher dose of VAY736, he or she must have tolerated the lower dose of VAY736 for at least two cycles of therapy (e.g., he or she must not have experienced at the lower dose pair originally assigned a toxicity of non-hematological CTCAE grade ≥ 2 for which relationship to study drug cannot be ruled out). Moreover, the new, higher dose level of VAY736 with which the patient is to be treated must be a dose that has completed evaluation in a dose-escalation meeting and that has not exceeded the MTD estimated by the Bayesian model given all available data.

Documented consultation with Novartis must occur prior to any intra-patient dose escalation occurring. These changes must be recorded on the Dosage Administration Record CRF.

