7.2.3.1 Pharmacokinetics and immunogenicity blood sample collection and handling

If the dosing of Cycle 3 Day 1 for VAY736 or Cycle 1 Day 8 for ibrutinib is delayed, the PK sampling for the full PK profile should be delayed until the dose of VAY736 or ibrutinib is administered. On the date of administration, the PK samples should be collected to match the scheduled time points for Cycle 3 as outlined in [Table 7-6](#) or [Table 7-7](#) for VAY736 or Cycle 1 in [Table 7-8](#) for ibrutinib.

Exact dates and actual PK blood draw times will be recorded on the appropriate eCRF. Any sampling problems (e.g. patient administrated with study drug before the PK blood draw took place) must be noted in the comments section of the eCRF and on appropriate source documentation.

If any of the scheduled sampling times are missed or a sample is not drawn according to this schedule, the actual collection date and time will be recorded and the remaining samples will be collected on schedule whenever possible.

If vomiting occurs within 8 hours following ibrutinib administration on the day of PK sampling, where post-dose time-points are collected, no additional study medication should be taken in an effort to replace the material that has been vomited. The time (using the 24-hour clock) of vomiting should be recorded in the Adverse Events eCRF.

Unscheduled PK samples should be collected if any of the following events occur:

- If a patient treated with investigational drugs experiences an AE that results in an unscheduled visit or fits the criteria of a SAE or DLT, as determined by the investigator.
- Whenever an ECG with a QTcF change from baseline > 60 ms or a new absolute QTcF ≥ 501 ms result is known. The exact time of sample collection should be noted in the unscheduled eCRF.
- In the event of other clinically significant AEs (such as infusion reaction/anaphylaxis) or if immunogenicity is suspected.
- During safety follow-up period either at or prior to end of safety follow-up period

Residual PK and IG serum or plasma samples used for PK and IG analysis may also be used for [REDACTED] metabolites and/or PD analyses related to VAY736 or ibrutinib therapy and cancer. If conducted, these results will be reported separately.

Refer to the [VAY736Y2102 Laboratory Manual] for detailed instructions for the collection, handling, and shipment of PK and immunogenicity samples.

Table 7-6 Pharmacokinetic blood collection log for VAY736 Q2W dosing (VAY736, IG, [REDACTED])

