2.8.4.4 Dose proportionality

The analysis of dose proportionality may be conducted for AUCtau and Cmax of VAY736 using a power model on log-transformed scale. The log-transformed PK parameters will each be regressed onto a fixed factor for log (dose). The 90% confidence interval (CI) of the slope for each PK parameter will be computed from the model and presented in the summary table.

Cmax and AUC will be used for dose proportionality analysis using the power model (Gough 1995). The power model empirical relationship between a PK parameter and dose is of the form

$$PK = \text{Exp}(\alpha)(\text{dose})^\beta,$$

where "PK" represents the PK parameter AUC or Cmax. For analysis, this equation is log-transformed (natural log), obtaining the equation

$$\log_e(PK) = \alpha + \beta \log_e(\text{Dose}),$$

The slope beta measures the dose-proportionality between Dose and the PK parameter.

To test for dose proportionality, the confidence interval criteria for assessment of dose proportionality from Smith et al. (2000) will be used. The *a priori* acceptance range for the slope, according to Smith, is given by:

$$1 + \frac{\text{Ln}(0.8)}{\text{Ln}(\text{dose_ratio})} < \beta < 1 + \frac{\text{Ln}(1.25)}{\text{Ln}(\text{dose_ratio})}$$

Where 1.25 and 0.8 are the critical *a priori* values suggested by regulatory authorities for any bioequivalence problem after a data log transformation, and "dose_ratio" is the ratio of the largest to the smallest dose. Dose proportionality can be claimed if the 90% confidence interval for the slope is entirely contained within this *a priori* range.

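### VAY736 PK data collected after an intra-patient dose escalation are summarised under the original, lower dose, because the SAP's pooling rule has no exception for PK

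*SAP*

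**What the plan says.** **Attribution rule.** SAP 2.1 states that for intra-subject escalation "data from before and after the change in dose will be listed and summarized together under the originally intended dose level/treatment group". The same section pools patients by VAY736 dose level and schedule for safety analyses, and counts PK and ADA among these. SAP 2.2.1 fixes treatment received by Cycle 1 dosing, so a later change does not move the patient to another group.

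**When escalation may happen.** Protocol 6.2.3.2: "Intra-patient dose escalation is not permitted at any time within the first two cycles of treatment". It continues: "After the second cycle is completed, individual patients may be considered for treatment at a dose of VAY736 that is higher" than the assigned one. The new dose level "must be a dose that has completed evaluation in a dose-escalation meeting".

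**PK sampling (Q2W, Protocol Table 7-6).** Full VAY736 profiles are drawn in Cycles 1 and 3. Cycle 4 has pre-dose and end-of-infusion samples. Pre-dose samples continue in Cycles 5 and 6, and in Cycles 7 and 8 where VAY736 continues. If the Cycle 3 Day 1 dose is delayed, the full profile moves with it, and "the PK samples should be collected to match the scheduled time points for Cycle 3" (Protocol 7.2.3.1).

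**PK analysis.** Protocol 10.5.4 summarises concentrations at each scheduled time point. SAP 2.8.4.3 lists derived parameters by treatment group. SAP 2.8.4.1 allows concentration data to be left out of parameter estimation for several reasons, but a dose change is not among those named. For the optional power model, SAP 2.8.4.4 says "The log-transformed PK parameters will each be regressed onto a fixed factor for log (dose"), without stating whether this is the assigned or the actual dose, or which cycle supplies the exposure.

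**The concern.** The purpose of a PK summary by dose is to describe exposure at that dose. Once a patient has been escalated, samples drawn under the higher dose carry no direct information about the lower one, yet the rule in SAP 2.1 places them there. The protocol foresees the event and the SAP covers it, so this is what the written plan would do, not a gap to be settled by judgement at analysis.

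At stake are the by-dose concentration summaries from Cycle 3 or 4 onward and, in a narrower case, the second-profile AUCtau and Cmax. The low-dose groups are small, so a single patient can move a geometric mean visibly. If the assigned dose were also the regressor in the power model, the slope would be pulled below its true value.

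**Working it through.** The plan gives no figure on this point to reproduce. The check is one of timing, followed by an illustration of size.

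**1. Which samples can be affected.** Cycles are 28 days, so Cycle 3 Day 1 is study day 2 × 28 + 1 = 57, the earliest possible date for a change.
- Change at Cycle 3 Day 1: the Cycle 3 profile after the pre-dose sample, and everything later, is at the higher dose.
- Change at Cycle 3 Day 15: the profile up to the Day 15 pre-dose sample is still at the original dose. The Day 15 end-of-infusion sample and the samples from Cycle 4 on are not.
- Change at Cycle 4 or later: the Cycle 3 profile is correctly attributed; only later concentrations are misplaced.

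**2. How likely a Cycle 3 Day 1 change is.** Protocol 6.2.3 requires that "Patients must complete a minimum of 1 cycle of treatment with the minimum safety evaluation and drug exposure", or have a DLT in that cycle, to count as evaluable. In sequential cohorts the next dose opens after about 28 days and needs about 28 more before it can be reviewed: 28 + 28 = 56 days with no enrolment or meeting lag, against day 57. With any real lag, a patient in an original cohort starts the Cycle 3 profile at the assigned dose. The exception is a patient enrolled later at a lower level: "Cohorts may be added at any dose level below the MTD" (Protocol 6.2.2). SAP 3.1.1 likewise allows extra cohorts to elaborate safety and PK. For such a patient the higher dose may already be cleared by day 57.

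**3. Effect on a low-dose geometric mean.** Assume exposure proportional to dose and one of n patients moved from 0.3 to 1 mg/kg. Inflation = (1/0.3)^(1/n) = 3.33^(1/n):

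| n | Inflation |
|---|---|
| 3 | 1.49 |
| 4 | 1.35 |
| 6 | 1.22 |

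In the first interval after a change, carry-over from the lower doses would make the effect somewhat smaller.

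**4. Effect on the power-model slope, if the assigned dose were used.** Assume 4/4/7 patients at 0.3/1/3 mg/kg. The total of 15 escalation patients is in the Amendment 06 study status; the split is an assumption. Assume a true slope of 1, no noise, and an affected profile.
- Mean log dose = [4(−1.204) + 4(0) + 7(1.099)]/15 = 0.192. The sum of squares about this mean, Sxx, is 13.70.
- Shift in slope = (log assigned dose − 0.192) × ln(dose ratio)/Sxx.
- One patient 0.3 to 1 mg/kg: (−1.204 − 0.192) × 1.204/13.70 = −0.123, so the slope is 0.877. Two such patients: 0.755.
- One patient 1 to 3 mg/kg: (0 − 0.192) × 1.099/13.70 = −0.015, so the slope is 0.985.
- With equal groups and one patient moved from 0.3 to 1 mg/kg: 0.82 (n = 3), 0.87 (n = 4), 0.91 (n = 6).

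The SAP 2.8.4.4 acceptance range for a tenfold dose ratio is 1 + ln(0.8)/ln(10) = 0.903 to 1 + ln(1.25)/ln(10) = 1.097.

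**5. What the SAP criterion judges.** It requires the whole 90% CI to lie inside that range. With 4/4/7, correct attribution and an estimated slope of exactly 1, the half-width is t(0.95; 13 df) × √[ln(1 + CV²)/Sxx]: 0.095, 0.118 and 0.140 for an assumed CV of 20%, 25% and 30%. The half-width allowed is 0.097.

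**The case against.** The strongest case on the other side has four parts.

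- **The Cycle 3 profile is a narrow case.** A reader might infer that every escalated patient's full Cycle 3 profile is misattributed. The documents do not support that, for the timing reasons shown. This part stands and limits the point.
- **Bias in dose proportionality is not established.** A reader might infer that the plan would produce a false departure from proportionality. But the analysis is optional, and SAP 2.8.4.4 names neither the dose nor the cycle. AUCtau is defined both after first dose and at steady state, and Cycle 1 profiles cannot be affected. The slope of 0.877 is the high-leverage case and a point estimate. At a CV somewhat above 20%, proportionality could not be claimed even with perfect attribution; Protocol 1.2.3.2 calls variability moderate without giving a figure. This part also stands.
- **AE grouping is a convention.** A reader might infer that the AE tables are wrong because later events at a higher dose are counted at the lower one. Grouping by original dose agrees with the treatment-received definition in both documents. SAP 2.5.1.1.1 lists all administered doses by patient and SAP 2.8.2.1.2 lists all AEs, so dose at onset can be traced. The convention is defensible.
- **Nothing that drives dose selection through DLTs is touched.** Escalation is barred in Cycles 1 and 2, so DLTs, the BLRM and the MTD are unaffected. This stands.

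None of this answers the remaining point. Concentrations after the change are still summarised under the old dose, and the discretionary exclusion in SAP 2.8.4.1 does not name that situation.

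**Conclusion.** The point holds for PK, conditionally. If any patient was escalated after Cycle 2, SAP 2.1 as written places later VAY736 concentrations in the summaries of a dose no longer being given. It places the Cycle 3 AUCtau and Cmax there only when the change was made at or before Cycle 3 Day 1. In a group of 3 to 6, one patient moved from 0.3 to 1 mg/kg would inflate the low-dose geometric mean by roughly 20% to 50%, assuming dose-proportional exposure.

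For dose proportionality the finding is an ambiguity: which dose and which cycle enter the model is unstated, and a changed conclusion is possible but not demonstrated. The MTD and the main AE tables do not need to change. The documents do not say whether any patient was escalated, so the practical effect may be nil. PK is a secondary objective, and the correction is worth making chiefly because it is specific and nearly free.

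**What to change.** In SAP 2.1, add a PK exception to the intra-subject escalation rule. In SAP 2.8.4, state that:

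- VAY736 concentrations and PK parameters obtained after an escalation are summarised by the dose actually given at that sample or profile, or are excluded from the original-dose summaries;
- the power model uses the dose actually given for the profile analysed, and the cycle is named.

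Optionally, flag AEs with onset after escalation with the actual dose in the AE listing. Keep original-dose grouping for the main AE tables and the other summaries.

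The cost is a few SAP sentences and one derived variable, dose at sample, available from administered doses that are already recorded. No new data are needed. If the dosing records show that no patient was escalated, a sentence saying so closes the point.
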